We propose a nationwide randomized clinical trial in which smokers (N=660) receive samples of cigarette-like e-cigarettes (n=440) vs. not (n=220). Randomization will be 2:1 to increase precision of uptake outcomes, broadly but concretely defined (Aim 1). A subset of smokers (n=120) will be recruited locally, to assess the impact of e-cigarette use on biomarkers of exposure (Aim 2). Finally, though ours is not a cessation study, it would be a missed opportunity if we did not track cessation outcomes (Aim 3) or sufficiently power the trial to detect differences if they emerge. Thus, our study is designed and powered to address a comprehensive set of outcomes along three domains: 1) uptake and patterns of use, 2) biomarkers of exposure, and 3) changes in smoking, all captured during the switching process while it naturally occurs in real time.

Aim1: Describe rates and patterns of naturalistic uptake of e-cigarettes among smokers. We examine a broad set of uptake indicators, including trial, repeat trial, regular use, and purchase, and the time course and predictors for each. Hypothesis 1a: Within the e-cigarette group, we hypothesize that at least 90% of smokers will try the product at least once, 45% will use regularly (at least 4/7 days, at any time during follow-up), 25% will use daily for ≥ 7 days (at any time during follow-up), 25%/10% will be using at least some/daily at final follow-up, and 20% will independently purchase e-cigarettes. Hyp 1b: Among smokers in the e-cigarette group, 40% will show a minimum of 50% reduction in cigarettes per day, and as a group, e-cigarette users will show greater decreases in cigs/day as compared to control. **Aim2: Assess the impact of e-cigarette use on biomarkers of exposure, to determine if smokers self-titrate to nicotine as they switch products.** Within a subset of locally recruited smokers, we hypothesize (Hyp 2) that use of e-cigarettes will lead to significant short-term (1 month) decreases in CO & NNAL, but no net change in cotinine. **Aim3: Assess concurrent and downstream (over 6 months) effects of e-cigarette use on smoking behavior.** Consistent with most prior research, we hypothesize that provision and use of e-cigarettes (vs. control group) will lead to (Hyp 3a) higher rates of quit attempts, (Hyp 3b) cessation, and (Hyp 3c) increases in motivation/confidence to quit. This is not a cessation trial but is positioned to evaluate important cessation outcomes in a naturalistic setting.

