Sample size estimate for local subset, to capture biomarkers of exposure We searched for prospective e-cigarette studies (controlled or not) that were NOT cessation based but reported on biomarkers, either CO or cotinine. We found only one (47) but acute decreases (within 1 month) in CO were only indirectly reported (in graph, separated by smoking group outcomes). Consistent with those data, we expect an overall decrease in CO within 1month of 35%, compared with no such decreases within the control group. A sample size of 80 in the e-cigarette local subset group (total of n=120 for the local subset who complete the baseline in-person lab visit) will have at least 80% power to detect a 35% decrease in CO (23.5ppm to 15.3ppm in the e-cigarette group vs. no change in the control group, assuming a standard deviation of 15.0 in the control group and 10.0 in the e-cigarette group (standard deviations were estimated from the interquartile ranges reported in the Polosa study (47) using standard procedures (134)). We expect no group differences in cotinine. We recognize that this technically implies a test of equivalence, and we are willing to accept up to +/-3% difference to conclude equivalence. With a local subset sample size of n=120 (40 control and 80 e-cigarette), $\alpha=0.05$, a two-sided t-test has >90% power to reject the null hypothesis that the two groups are not equivalent (1400ng/ml +/- 45ng/ml) in favor of the alternative hypothesis that the mean cotinine levels of the two groups are equivalent (assuming an expected difference in means of 0ng/ml and a common standard deviation of 70.0ng/ml) (135).

Statistical Considerations – Data Analyses

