Hyp1b: Among smokers in the e-cigarette group, 40% will show a minimum of 50% reduction in cigarettes per day, and as a group, e-cigarette users will show greater decreases in cigs/day as compared to control. Reduction of cigarettes per day will be calculated based on the TLFB at baseline and 6 months for both groups, with “reducers” defined as those that reduce cigarettes per day by $\geq 50\%$. We will estimate the mean reduction, 95% confidence interval on the reduction, and the proportion of those that are considered “reducers” in both groups, the latter tested via a chi-square test with $\alpha=0.05$ two-sided significance level.

Hyp2: Within a subset of locally recruited smokers, we hypothesize that use of e-cigarettes will lead to significant decreases in CO and NNAL, but no net change in overall nicotine exposure. Changes in CO, NNAL and cotinine will be calculated based on the baseline, 1, and 6-month measurements. Mean change in CO/NNAL (thru 1 and 6 months) will be compared via a two-sample t-test with $\alpha=0.05$ significant level. In order to test equivalence for change in cotinine between the two groups, the TOST procedure (137) will be followed where two one-sided tests will be used to test that the difference in the change between groups (Δ) is within the +/-3% bounds that we are willing to accept ($H_{01}: \Delta < -3\%$; $H_{02}: \Delta < +3\%$). If Δ is contained completely within the +/-3% bounds, then equivalence will be concluded. We will use an $\alpha=0.05$ significance level.

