Hyp1b: Among smokers in the e-cigarette group, 40% will show a minimum of 50% reduction in cigarettes per day, and as a group, e-cigarette users will show greater decreases in cigs/day as compared to control. Reduction of cigarettes per day will be calculated based on the TLFB at baseline and 6 months for both groups, with “reducers” defined as those that reduce cigarettes per day by $\geq 50\%$. We will estimate the reduction, 95% confidence interval on the reduction, and the percent of those that are considered “reducers” in both groups, the latter tested via a chi-square test with an $\alpha=0.05$ two-sided significance level.

Hyp2: Within a subset of locally recruited smokers, we hypothesize that use of e-cigarettes will lead to significant decreases in CO, but no net change in overall nicotine exposure. Changes in CO and cotinine will be calculated based on the baseline, 1, and 6-month measurements. Change in CO (thru 1 and 6 months) will be compared via a two-sample t-test with $\alpha=0.05$ significant level. In order to test equivalence for change in cotinine between the two groups, the TOST procedure (137) will be followed where two one-sided tests will be used to test that the difference in the change between groups (Δ) is within the $\pm 3\%$ bounds that we are willing to accept ($H_{01}: \Delta < -3\%$; $H_{02}: \Delta < +3\%$). If Δ is contained completely within the $\pm 3\%$ bounds, then equivalence will be concluded. We will use an $\alpha=0.05$ significance level.

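### The t-test for change in CO and NNAL has no stated variance form, and at the plan's own CO standard deviations a pooled test would be anti-conservative

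*Combined protocol and SAP*

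**What the plan says.** The analysis is described twice. Under Statistical Considerations – Data Analyses, Hyp2: "Mean change in CO/NNAL (thru 1 and 6 months) will be compared via a two-sample t-test", at alpha 0.05. In the Data and Safety Monitoring Plan, section 9 (Data Analysis Plan), Hyp2, the same sentence appears for CO alone: "Change in CO (thru 1 and 6 months) will be compared via a two-sample t-test". Neither place says whether the variances are pooled, and neither states sidedness for these tests.

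The inputs are in the paragraph on the local subset under Statistical Considerations – Sample Size & Power. The arms are given there: "With a local subset sample size of n=120 (40 control and 80 e-cigarette". The CO scenario is "23.5ppm to 15.3ppm in the e-cigarette group vs. no change in the control group", with the calculation done "assuming a standard deviation of 15.0 in the control group and 10.0 in the e-cigarette group". The resulting claim is that 80 e-cigarette participants "will have at least 80% power to detect a 35% decrease in CO". The SDs are said to come from interquartile ranges in a cited observational study. The text does not say whether they describe CO levels or changes in CO. For cotinine, the same paragraph uses one common SD. No SD is given for NNAL.

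The opening of the Data Analyses section leaves transformations to be decided after exploratory work. It has no rule for unequal variances.

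**The concern.** A pooled t-test estimates one variance and weights each arm by its size. If the larger arm is the less variable one, the pooled variance is pulled down and the standard error of the difference comes out too small. The plan's CO assumptions have this pattern, and the 2:1 allocation removes the protection that equal arms would give.

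Two things are at stake. The first is the reported precision of the main Aim 2 contrast: its p-value and any interval given with it. The second is pre-specification. At the plan's own inputs the two usual forms of the test differ materially, and the text allows the choice to be made after the data have been seen.

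**Working it through.** **Inputs.** Arms 40 control and 80 e-cigarette; CO SD 15.0 and 10.0 ppm; effect 23.5 − 15.3 = 8.2 ppm against no change; alpha 0.05, taken as two-sided (an assumption).

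**1. The plan's power figure.** Standard error with separate variances: √(15²/40 + 10²/80) = √(5.625 + 1.25) = √6.875 = 2.622. Satterthwaite degrees of freedom: 6.875² / (5.625²/39 + 1.25²/79) = 56.9. Noncentrality: 8.2/2.622 = 3.13.

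- Welch t-test: power 86.7%.
- Normal approximation with the same standard error: 87.8%.
- A common SD of 15 in both arms: 80.6%.

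All three meet the claim of 80% or more. The claim therefore reproduces, but it does not show which form the authors had in mind.

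**2. The pooled test at the same inputs.** Pooled SD: √[(39 × 225 + 79 × 100)/118] = √141.3 = 11.89. Pooled standard error: 11.89 × √(1/40 + 1/80) = 2.302. The true value is 2.622, so the ratio is 0.878.

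- Large-sample size with equal means: the critical value 1.980 shrinks to an effective 1.980 × 0.878 = 1.74, and the two-sided tail beyond that is 8.2%.
- Exact size, integrating over the two sample variances: 8.52%. Simulation with 400,000 trials: 8.53%.
- Welch in the same simulation: 4.98%.
- The pooled size stays at 8.5% with 36/72 or 50/100, so sample size does not cure it.

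**3. Coverage at the planned effect.** A shift in means does not alter the error in the standard error. With an 8.2 ppm difference and SDs 15 and 10, the pooled 95% interval covers 91.5% in simulation and the Welch interval 95.0%.

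**4. If 15 and 10 are follow-up SDs.** The analysed quantity is change, with variance b² + f² − 2rbf for baseline SD b, follow-up SD f and correlation r. The documents give neither b nor r, so I assume b equal in the two arms, from 10 to 15, and r from 0 to 0.8. Example with b = 15 and r = 0.5: control √(225 + 225 − 225) = 15.0; e-cigarette √(225 + 100 − 150) = 13.2.

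| b | r | SD of change, control / e-cigarette | pooled size |
|---|---|---|---|
| 15 | 0 | 21.2 / 18.0 | 6.3% |
| 15 | 0.5 | 15.0 / 13.2 | 6.0% |
| 15 | 0.8 | 9.5 / 9.2 | 5.2% |
| 12 | 0.5 | 13.8 / 11.1 | 6.7% |
| 10 | 0 | 18.0 / 14.1 | 7.0% |
| 10 | 0.8 | 9.2 / 6.3 | 8.3% |

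The range is about 5.2% to 8.3%.

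**5. If the product does nothing.** Randomised arms then share one distribution, the SDs are equal, and the pooled test has size 5.0%.

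**6. What Welch costs.** Power is 86.7% at 40/80 and 82.9% after a 10% loss (36/72). That loss is the trial-wide allowance; none is stated for the local subset. With equal SDs of 10, 12 or 15, simulated power falls by less than 0.5 percentage points against the pooled test. These power figures assume that 15 and 10 are SDs of change. On the step 4 reading, power depends mainly on the unknown correlation, whichever form of the test is used: Welch power runs from 54% (b = 15, r = 0) to over 99% (b = 10, r = 0.8).

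**The case against.** A reader might infer that the plan's nominal 5% test for CO and NNAL actually runs at 8 to 9%, so that false reductions will be claimed too often. The documents do not support that, for three reasons.

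- They never say pooled. The term two-sample t-test covers the Welch form, and entering separate SDs for CO next to a common SD for cotinine suggests that the authors saw the difference. This stands: the fault is an unspecified form, and no wrong form has been chosen.
- The SDs belong to the scenario in which CO falls, and they are not labelled as SDs of change. With no effect at all, the SDs are equal and the size is 5%. To reach 8.5% under equal means, the product would have to change the spread of CO change without moving its mean. This also stands for type I error. It does not dispose of the coverage result, which applies in the plan's own expected scenario.
- No NNAL SD is given, so the CO figure cannot be carried over. This stands in full.

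It can also be said that the Hyp2 text promises no confidence interval for CO or NNAL, and that an effect of 8.2 ppm, about 3.1 true standard errors, would usually be significant under either form. Both are fair and limit the practical stakes. The planned exploratory checks help only in part: they concern transformations, and they are made after the data are seen.

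**Conclusion.** The concern holds in conditional form. The plan leaves open the variance form of the CO and NNAL tests, while its own CO inputs put the larger SD in the smaller arm. If those SDs apply to change and the pooled form is used, the CO test has a size of about 8.5% with equal means, and its 95% interval covers about 91.5% at the planned effect. If they are follow-up SDs, the size is about 5.2% to 8.3% on the stated assumptions about baseline SD and correlation. Under a strict no-effect null it is 5%. Across these readings the pooled test is at or above its nominal level and never conservative. No figure can be given for NNAL; the recommendation covers it only because the same sentence governs both markers. All sizes assume normal data and two-sided testing.

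**What to change.** In both descriptions of Hyp2 (the Data Analyses section and section 9 of the Data and Safety Monitoring Plan), replace the unspecified t-test with a regression of follow-up CO on group and baseline CO, with heteroscedasticity-robust standard errors in a small-sample form such as HC3. Specify the same model for NNAL where it is analysed. Section 9 already adjusts motivation and confidence to quit for their baseline values, so this follows the plan's own practice. At minimum, name the Welch t-test. State that the tests are two-sided, and say in the sample size paragraph whether 15.0 and 10.0 are SDs of level or of change.

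The cost is a sentence or two in each place. Baseline values are already collected and no further participants are needed. On the plan's inputs the power claim holds under Welch, and the loss if the SDs prove equal is negligible.

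### Hypothesis 2 is stated, and CO sized, at 1 month, but the biomarkers are analysed at 1 and 6 months with no deciding time point or success rule

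*Combined protocol and SAP*

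**What the plan says.** All references are to the combined protocol and SAP.

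- **Specific Aims, Aim 2.** The hypothesis is that "use of e-cigarettes will lead to significant short-term (1 month) decreases in CO & NNAL, but no net change in cotinine". Aim 3, in the same section, is given a 6-month horizon, so the 1-month limit in Aim 2 looks deliberate.
- **Sample Size & Power, paragraph on the local subset.** For CO, "we expect an overall decrease in CO within 1month of 35%, compared with no such decreases within the control group". The subset "will have at least 80% power to detect a 35% decrease in CO (23.5ppm to 15.3ppm in the e-cigarette group", "assuming a standard deviation of 15.0 in the control group and 10.0 in the e-cigarette group". Cotinine equivalence is given more than 90% power with 40 control and 80 e-cigarette participants, without a time point. NNAL has no power figure.
- **Data Analyses, Hyp2.** The hypothesis is restated without the 1-month limit. Changes in all three markers are calculated at 1 and 6 months. "Mean change in CO/NNAL (thru 1 and 6 months) will be compared via a two-sample t-test with" a 0.05 level. The two one-sided tests (TOST) for cotinine are also at 0.05, with no time named.
- **Data and Safety Monitoring Plan, item 9, Hyp2.** The same analysis appears without NNAL: "Change in CO (thru 1 and 6 months) will be compared via a two-sample t-test with" a 0.05 level.
- **Data and Safety Monitoring Plan, item 2.** Uptake is the primary outcome. Biomarkers are listed among the outcomes of the six-month follow-up.

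**The concern.** A hypothesis set at one time is analysed at two, each at full alpha. The plan does not say that 1 month decides, or whether Hypothesis 2 needs all of its parts or only one. A 6-month result could therefore be reported as supporting or contradicting a 1-month hypothesis.

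The two times do not ask the same question. Aim 2 asks whether smokers adjust their nicotine intake as they switch products. Product is supplied for about 4 weeks, and Hypothesis 1a predicts that 25% of the e-cigarette group will be using at least some, and 10% daily, at final follow-up. Similar cotinine in the two arms at 6 months may only show that most participants no longer vape. The missing-data rule pushes the same way. Baseline values are substituted, and the plan itself notes that this shrinks group differences. That is conservative for a difference test but favours an equivalence conclusion.

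**Working it through.** **1. The plan's own power figures.**

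CO inputs: fall 23.5 − 15.3 = 8.2 ppm; SD 15.0 (n = 40) and 10.0 (n = 80); 0.05, taken as two-sided because the plan does not state sidedness for this test.
- SE = √(15²/40 + 10²/80) = √(5.625 + 1.25) = 2.622.
- Power = Φ(8.2/2.622 − 1.96) = Φ(1.167) = 87.8% (86.7% with a Welch t-test). The stated 80% or more holds.

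Cotinine inputs: margin ±45 ng/ml, SD 70, true difference 0.
- SE = 70 × √(1/40 + 1/80) = 13.56.
- Power = 2Φ(45/13.56 − 1.645) − 1 = 90.6% (90.2% with t). The stated figure of over 90% holds. With exactly 3% of 1400, which is 42 ng/ml, it would be 85.4%.

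**2. Error for one marker if either time counts.**
- Independent tests: 1 − 0.95² = 9.75%.
- Simulation, 500,000 draws, assumed correlation between times: 9.1% at 0.5, 8.4% at 0.7, about 7.1% at 0.9.
- Cotinine TOST, if run at both times with the true difference on the margin: 9.8% independent, 8.8% at 0.5, 7.5% at 0.8.

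**3. Error if any one of the four CO/NNAL tests counts.**
- Independent: 1 − 0.95⁴ = 18.5%.
- Equal correlation among all four: 15.6% at 0.5, 11.4% at 0.8.
- Counting only false decreases: 9.6% independent, 7.8% at 0.5, 5.7% at 0.8, against 2.5% for one test.

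**4. Error if CO and NNAL must both succeed at the same time, at either time.**
- Both markers null: 0.4–3.3% over assumed correlations of 0–0.9 between times and 0–0.7 between markers.
- One marker with a large true effect: the other is in effect tested twice, so at most about 9.75%.

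The documents give no correlations, so every correlated figure is a range under assumption.

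**5. Dilution of cotinine at 6 months.** Assume the predicted 25% applies to the local subset and that non-users' cotinine change matches control. The mean arm difference is then 0.25 times the difference among users. A 3% margin on the mean corresponds to 3%/0.25 = 12% among users, so users could differ by just under 12% and the arms would still lie inside the margin.

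**6. Baseline substitution.** Suppose 10% are missing in each arm (the plan's attrition allowance) and missingness is unrelated to cotinine. The arm difference is then multiplied by 0.9, so a true difference of 45/0.9 = 50 ng/ml would have an expected value of 45. This applies at 1 month too, in proportion to the data missing then.

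**The case against.** The strongest reply is that Hyp2 in the analysis section is the hypothesis that Aim 2 dates to 1 month. CO is sized there, so 6 months is added follow-up that merely lacks a label. This is a fair reading, but the text does not secure it. The restated hypothesis drops the limit, and the 6-month tests sit in the same sentence as the 1-month tests. The plan does label secondary analyses under Hyp 3 and has an ancillary section, and the 6-month biomarker tests appear under neither.

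A second reply is that Hypothesis 2 reads as a conjunction: CO and NNAL fall, and cotinine does not change. On that reading there is no inflation across markers, only across times. That stands, and it limits the problem. The plan does not state the rule, though.

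A reader might infer that the family-wise error is about three times a stated 5%. The documents do not support this. Their 0.05 is a per-test level, with no family-wise promise. The multiple depends on correlations they do not give and on letting any single rejection count. Nor is the whole hypothesis powered at 1 month: only CO is, explicitly. That the TOST is run twice is also an inference, because no time is named.

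The dilution point should not be overstated either. Participants may keep leftover product, and 20% are predicted to buy their own.

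**Conclusion.** The mismatch is real and can be read directly from the text. Its cost depends on a success rule that the plan leaves open: up to 9.75% per marker if either time counts, and up to 18.5% if any of the four CO/NNAL tests counts, falling to about 11–16% at assumed correlations of 0.8–0.5. If CO and NNAL are both required, only the choice between times remains.

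The interpretive risk for cotinine does not depend on those error rates. At 6 months, equivalence is a weak sign of self-titration if most participants have stopped using the product.

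Biomarkers are not the declared primary outcome, so this is a change that should be made, not a threat to the trial's main result.

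**What to change.** In the Data Analyses section and in item 9 of the Data and Safety Monitoring Plan:

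1. Name 1 month as the deciding time point for Hypothesis 2 for CO, NNAL and the cotinine TOST.
2. State that Hypothesis 2 is supported only if CO and NNAL both fall and cotinine is equivalent at 1 month, each tested at 0.05. Because all three are required, no testing order or alpha split is needed.
3. Report 6-month comparisons as secondary, with estimates and confidence intervals.
4. Use the same marker list, including NNAL, in both places.

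**Cost.** This is wording only, with no new data. The 6-month results lose confirmatory status. CO power (about 87–88%) and cotinine power (about 90% at ±45 ng/ml) are unchanged. By comparison, splitting alpha over the two times (0.025 each) would lower them to 81.2% and 82.6% by the same normal formulas.

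Full support does become harder to reach. The chance that CO and cotinine both succeed is 0.878 × 0.906 = 79.6% if independent. It is at least 0.878 + 0.906 − 1 = 78.4% and at most 87.8% whatever their correlation. That is before NNAL, for which the plan gives no power.

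### The second null of the cotinine equivalence test is printed in the wrong direction, and its decision sentence names no confidence interval

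*Combined protocol and SAP*

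**What the plan says.** The test is described under Hyp2 in Statistical Considerations – Data Analyses, and again in nearly the same words under Hyp2 in section 9 (Data Analysis Plan) of the Data and Safety Monitoring Plan.

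- Method: "the TOST procedure (137) will be followed".
- Purpose: "two one-sided tests will be used to test that the difference in the change between groups (Δ) is within the +/-3% bounds".
- Nulls, with the same signs in both places: "H_{01}: \Delta < -3\%$; $H_{02}: \Delta < +3"%.
- Decision, main analysis section: "If Δ is contained completely within the +/-3% bounds, then equivalence will be concluded".
- Decision, monitoring plan: "If Δ is contained completely within the $\pm 3\%$ bounds, then equivalence will be concluded".
- Level: "We will use an $\alpha=0.05$ significance level".

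The sample size section for the local subset sets the margin: "we are willing to accept up to +/-3% difference to conclude equivalence". There the null is given in words, correctly, as the groups not being equivalent. More than 90% power is claimed for a margin of 45 ng/ml around 1400 ng/ml, a true difference of 0, a common SD of 70 ng/ml, and 40 control and 80 e-cigarette participants. The test is called a two-sided t-test.

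Neither statement of the analysis gives the direction of subtraction for Δ, says whether 0.05 applies to each one-sided test, or mentions a confidence interval for the equivalence decision.

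**The concern.** A TOST needs one null below the lower bound and one above the upper bound, so that rejecting both places Δ between them. Here both nulls are of the less-than kind. The first is contained in the second, so rejecting both is the same as rejecting the second alone, and the conclusion would be that Δ is at or above +3%.

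The decision sentence does point towards equivalence, but it does not supply a test. Δ has just been defined as the between-group difference in change, and the sentence asks whether Δ lies within the bounds. An estimate inside the bounds is weaker evidence than an interval inside them.

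This test decides the cotinine half of Hyp 2, that total nicotine exposure does not change as smokers take up e-cigarettes. In an equivalence claim a loose rule favours the hoped-for answer, so the hypotheses and the decision rule need to be exact and to agree with each other.

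**Working it through.** **Inputs** (sample size section, local subset): SD 70 ng/ml; 40 control, 80 e-cigarette; margin ±45 ng/ml; true difference 0; α = 0.05. That section attaches the SD to mean cotinine levels; here it is assumed to apply to change. Exactly 3% of 1400 is 42 ng/ml, and 45 is 3.2%.

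**Standard error:** 70 × √(1/40 + 1/80) = 70 × √0.0375 = 13.56 ng/ml, with 40 + 80 − 2 = 118 degrees of freedom.

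**1. The plan's own power, from a correctly signed TOST.** Normal approximation: 2Φ(margin/SE − z) − 1.

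- 0.05 per side: 45/13.56 = 3.320; 3.320 − 1.645 = 1.675; power = 2(0.953) − 1 = 90.6%. Integrating exactly over the sample SD gives 90.2%.
- 0.025 per side: 3.320 − 1.960 = 1.360; power = 2(0.913) − 1 = 82.6%; exact 81.7%.

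The claim of more than 90% reproduces at 0.05 per side, which corresponds to a two-sided 90% interval. It does not reproduce at 0.025 per side. At the exact 3% margin of 42 ng/ml and 0.05 per side, the exact power is 84.9%.

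**2. The printed nulls taken by themselves.** Rejecting H02: Δ < +3% requires an estimate above 45 + 1.658 × 13.56 = 67.5 ng/ml. The probability of rejecting both nulls is about 0.00004% when the arms are equal, 5% when Δ = +45, and 95.1% when Δ = +90 ng/ml (90/1400 = 6.4%). So the printed pair is a test for a difference above the upper bound.

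**3. The decision sentence applied to the point estimate.** P(declare) = Φ((margin − Δ)/SE) − Φ((−margin − Δ)/SE).

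- Δ = 0: 2Φ(3.320) − 1 = 99.9%.
- Δ = +45: Φ(0) − Φ(−90/13.56) = 0.50 − 0.00 = 50%.
- Δ = +90: 0.05%.

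The 50% hardly depends on the SD or on whether 45 or 42 is used. With the true difference on the bound, the estimate falls on either side of it equally often.

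**4. The corrected rule.** With the 90% interval required to lie inside ±45 ng/ml, equivalence is declared 5.0% of the time when Δ equals the margin and 90.2% when Δ = 0. With a sample SD of 70, the largest observed difference that passes is 45 − 1.658 × 13.56 = 22.5 ng/ml. The point-estimate reading would pass anything below 45.

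A simulation of 400,000 replicates agreed with the results in steps 2 to 4.

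**The case against.** The intended test is not in serious doubt. The plan names TOST, cites a methods reference for it, says the tests are to show that Δ lies within the bounds, and words the null correctly in the sample size section. Its power figure reproduces under a correctly signed test. An experienced statistician would probably run it properly. The first null already has the right direction, so a single sign is wrong. The monitoring plan largely repeats the main analysis text, so the second occurrence is weak evidence that the sign was deliberate, and an error in reading the symbol from the PDF cannot be ruled out. The wording of the decision sentence also suggests an interval, since a single number is not completely contained in anything, and an α level has no role in a rule based on the estimate alone.

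Most of this stands, and it limits the practical risk. It does not make the printed hypotheses right, and it does not supply the missing interval or its level. The power section speaks of a two-sided test and intervals elsewhere in the plan are 95%, so an analyst could reasonably choose a 95% interval here. That would give 81.7% power, below the stated figure.

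A reader might infer that the plan, as written, would reject equivalence when the arms are equal and accept it when e-cigarette cotinine is clearly higher. The documents do not support that. The reversal comes only from the printed nulls read in isolation. The decision sentence, even on the point-estimate reading, accepts equivalence 99.9% of the time at Δ = 0 and 0.05% at Δ = +90 ng/ml. Saying that the e-cigarette arm is the higher one also assumes a direction for Δ that the plan never gives.

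**Conclusion.** The point holds as two separate errors of specification. First, H02 is printed in the wrong direction in both places and contradicts the purpose, the decision sentence and the verbal null. Second, the decision sentence names no confidence interval. If it were applied to the point estimate, the chance of declaring equivalence at the margin would be about 50% instead of 5%. That figure is conditional on the reading, and the plan does not clearly adopt a 50% error rate. The SE of 13.6 ng/ml rests on taking the SD of 70 to apply to change, with all 120 local participants contributing. The 50% is insensitive to that assumption, but the power figures are not. The correction should be made, because it concerns the operative hypotheses and decision rule of an Aim 2 test. The naming of TOST argues against ranking it higher.

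**What to change.** Make the same change under Hyp2 in Statistical Considerations – Data Analyses and in section 9 of the Data and Safety Monitoring Plan:

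- Define Δ as e-cigarette minus control in the change in cotinine.
- State H01: Δ ≤ −3% and H02: Δ ≥ +3%, each tested one-sided at 0.05.
- Replace the decision sentence by: equivalence is concluded only if the two-sided 90% confidence interval for Δ lies entirely between −3% and +3%.

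The level of 0.05 per side is the one that matches the stated power. The cost is a wording change in two places, with no effect on data collection or sample size.
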